### 5 STUDY DESIGN

This is a Phase IV, interventional, open-label, multicenter, multinational study with 2 study periods (a run-in period of 4 weeks and an assessment period of 8 weeks) to assess efficacy and safety of the extemporaneous combination of Nebivolol and Amlodipine in Grade 1 - 2 hypertension patients versus each monotherapy.

The study will be conducted in approximately 25 investigational clinical sites in Bulgaria, Poland, and Ukraine. The total study duration is 12 weeks including a run-in period of 4 weeks and an assessment period of 8 weeks.

Screening Visit 1 (Week -4): At Visit 1, after providing the informed consent, patients with Grade 1 - 2 hypertension (SBP ranging from  $\geq$ 140 to  $\leq$ 179 mmHg and DBP ranging from  $\geq$ 90 to  $\leq$ 109 mmHg) who were on treatment with any BBs or CCBsc including NEB 5 mg or AML 5 mg for at least one month prior to Visit 1 will be screened for eligibility. The eligibility for Grade 1 - 2 hypertension will be based on the 2018 ESC/ESH guidelines, and the BP criteria is defined as mean sitting SBP  $\geq$ 140 mmHg and  $\leq$ 179 mmHg and/or mean sitting DBP  $\geq$ 90 mmHg and  $\leq$ 109 mmHg.

Run-in period from Visit 1 (Week -4) to Visit 2 (Week 0): On the same day of the Screening visit, the eligible patients will enter into a run-in period of 4 weeks after screening, during which:

- Patients receiving NEB 5 mg or AML 5 mg will continue the same therapy for 4 weeks.
- Patients on any other BBs or CCBsc will be switched to NEB 5 mg or AML 5 mg.

Patients entering this phase in therapy with NEB 5 mg or AML 5 mg should be in a 1:1 ratio.

Assessment period from Visit 2 (Week 0) to Visit 4 (Week 8): After 4 weeks ( $\pm$ 2 days) of run-in period of monotherapy, the BP will be further assessed (Visit 2). Patients with uncontrolled BP levels (sitting SBP/DBP  $\geq$ 130/80 mmHg) at Visit 2, with the treatment adherence (ranging between 80% to 120%) and who did tolerate the treatment will enter into the assessment period and will be assigned to the extemporaneous combination of NEB 5 mg

MENARINI	Corporate Medical Department		
	Protocol Template		
Identification Number	Version Number	State	Effective date
FORM-000050125	2.0, CURRENT	Effective	08 Jan, 2021

*Study Code:* MEIN/21/AmNe-Hyp/001

and AML 5 mg. Patients with controlled BP levels (sitting SBP/DBP <130/80 mmHg) and/or who do not tolerate the treatment or have an adherence range below 80% or above 120%, will be withdrawn from the study.

After 4 weeks  $\pm 2$  days in the assessment period, patients BP will be further evaluated at Visit 3: patients with controlled BP levels (sitting SBP/DBP <130/80 mmHg) will continue the same extemporaneous combination, while patients with uncontrolled BP levels will be uptitrated from extemporaneous combination NEB/AML 5/5 mg to extemporaneous combination of NEB/AML 5/10 mg for further 4 weeks.

At the end of the assessment period (8 weeks  $\pm 4$  days), the patients will attend an End of Treatment Visit 4. To correctly evaluate the additional effect of the combination therapy, the number of patients with uncontrolled BP on NEB or AML monotherapy needs to be balanced at Visit 2. In order to maintain a 1:1 ratio during the assessment period, a cap of 110 patients for each treatment arm (ie. NEB and AML) will be included at Visit 2 in order to maintain a balanced number of uncontrolled patients entering the assessment period for each drug. The evaluation will be done every 50 patients. If the rate of entrance in the assessment period for one of the 2 tested drugs will deviate more than 5%, a corrective measure will be initiated: according to the enrolment site statistics, one or more sites will be informed to enroll a greater number of patients being treated with the least represented drug in the assessment period.

A total number of 290 patients will be screened considering 25% of drop-out rate, to obtain approximately 216 completed patients at the end of the study (Visit 4).

Sitting BP will be measured at all visits before blood sampling. BP will be measured in both arms at the Screening visit (Visit 1) in order to detect possible between-arm differences. The arm with the higher mean DBP will be used in all subsequent visits for BP assessment. Blood pressure measurements should be performed as nearly as possible within the same time frame of the day (7:00 to 12:00 a.m.), on the same arm, possibly by the same member of the site staff/personnel, and using the same calibrated equipment at each visit.

Patients should be seated comfortably in a quiet environment for 5 minutes before beginning BP measurements. Three BP measurements will be recorded, 1 to 2 minutes apart, and additional measurements only if the first two readings differ by >10 mmHg. The mean of the

MENARINI	Corporate Medical Department			
	Protocol Template			
Identification Number	Version Number	State	Effective date	
FORM-000050125	2.0, CURRENT	Effective	08 Jan, 2021	

Study Code: MEIN/21/AmNe-Hyp/001

three recordings in sitting position will be used as the BP value for that visit. All BP measurements during the treatment phase will be performed as through readings (ie. 24 + 2 hour after the last drug intake). Study medication should be administered/consumed on the same time every day during the study; except the days of site visits, when study medication should be administered after all assessments mentioned as per study flow chart (Section 2.2). At Visit 1 (Week -4) and Visit 4 (Week 8), a 12-lead ECG will be performed.

Safety (AEs, SAEs) will be measured at all visits. In case of any abnormality of clinically relevant safety finding at any of the visits according to the Investigator, the patient will be contacted over phone within 24 hours to ensure their safety. Any patient having an ongoing AE or SAE at Visit 4, will be followed-up for further 2 weeks over a phone call.

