	To test the covariate effects and the effects of interactions between covariates on the primary efficacy endpoint (change in mean sitting DBP) as well as the first secondary efficacy endpoint (change in mean sitting SBP), a repeated measures general linear model (GLM) will be proposed. The GLM repeated measures procedure provides analysis of variance when the same measurement is made several times on each patient. Age, gender, body mass index, and baseline DBP will be included in the GLM model as covariates. The GLM model will be explained in detail in the Statistical Analysis Plan, approved before database lock.
	All the other continuous secondary/exploratory endpoints will be assessed across different study visits using a paired t-test or independent t-test, as applicable.
	All secondary/exploratory endpoints related to proportion of patients achieving the BP goal at Week 4 and Week 8 will be analyzed descriptively along with the relative 95% CI to assess if there is a significant difference from Week 0 where all patients were uncontrolled.
	Sample size : A total sample size of 216 patients is required to achieve 90% power at a 5% significance level assuming a difference in mean DBP from baseline (Visit 2) to 8 weeks (Visit 4) of 4 mmHg and a standard deviation for this difference of 10 mmHg. The mean change in DBP for the null hypothesis is set equal to 2 mmHg.

[figure not shown]
MENARINI	Corporate Medical Department		
	Р	Protocol Template	
Identification Number	Version Number	State	Effective date
FORM-000050125	2.0, CURRENT	Effective	08 Jan, 2021

A total number of 290 patients will be screened considering 25% of
drop-out rate, to obtain approximately 216 completed patients at the
end of the study (Visit 4).

MENARINI	Corporate Medical Department				
	Pr	otocol Template			
Identification Number	Version Number	State	Effective date		
FORM-000050125	2.0, CURRENT	Effective	08 Jan, 2021		

Study Code: MEIN/21/AmNe-Hyp/001

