## **12.2 Determination of Sample Size**

Considering a screen failure and a drop-out rate of 25% from Visit 1 to Visit 4 (End of Treatment), the number of patients to be screened are 290. Two-hundred and sixteen patients with uncontrolled hypertension, are planned to be included at screening in the assessment period lasting for 8 weeks. A total sample size of 216 patients is required to achieve 90%

NENARINI	Corporate Medical De		rtment	
	P	rotocol Template		
Identification Number	Version Number	State	Effective date	
FORM-000050125	2.0, CURRENT	Effective	08 Jan, 2021	

Study Code: MEIN/21/AmNe-Hyp/001

power at 5% significance level assuming a difference in mean DBP from baseline to 8 weeks of 4 mmHg and a standard deviation (SD) for this difference of 10 mmHg. The mean change in DBP for null hypothesis is set at 2 mmHg.

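### The Visit 2 cap of 110 patients per run-in drug is not reconciled with about 216 completers: at most 220 can start the combination, leaving room for about 4 (1.8%) without usable DBP data.

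*Protocol*

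**What the plan says.** Protocol Section 5 limits entry to the assessment period: "a cap of 110 patients for each treatment arm (ie. NEB and AML) will be included at Visit 2". The reason given is balance: "In order to maintain a 1:1 ratio during the assessment period". The synopsis and SAP 3.1 carry the same cap.

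The recruitment target follows in the same section: "A total number of 290 patients will be screened considering 25% of drop-out rate, to obtain approximately 216 completed patients", counted at Visit 4. The synopsis and SAP 3.1 repeat it.

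Section 12.2 pools the losses into one rate: "Considering a screen failure and a drop-out rate of 25% from Visit 1 to Visit 4". It then attaches the 216 to a different stage: "Two-hundred and sixteen patients with uncontrolled hypertension, are planned to be included at screening in the assessment period lasting for 8 weeks". The synopsis ties the same number to power: "A total sample size of 216 patients is required to achieve 90% power at a 5% significance level".

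No section gives a separate loss rate for Visit 2 to Visit 4. The mITT set (Protocol 12.3, SAP 5.2) requires baseline and Week 8 DBP. SAP 16.1.3 also restricts the primary analysis to patients with DBP at both Week 4 and Week 8. Nothing is imputed (Protocol 12.5.8, SAP 7.3).

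**The concern.** The cap counts patients entering the assessment period, while the target counts patients finishing it. With 220 as the ceiling at entry and about 216 expected 8 weeks later, almost no attrition is allowed for. The plan itself foresees losses after Visit 2: withdrawal of Grade 3 patients at Visit 3 (Section 2.1), withdrawal for adverse events, non-compliance or prohibited medication (Section 10), and loss to follow-up (Section 11).

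The stated sample size and its 90% power are at stake. A site or CRO that applies the cap literally closes entry at 110 per drug whatever happens later, and the number analysed then probably falls below the number on which the power statement rests. The double use of 216 in Section 12.2 hides this. Read as entrants, 216 fits under the cap, but the plan then has no allowance for loss on the combination.

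**Working it through.** **Inputs.** Cap of 110 per drug, two drugs (Section 5). 290 screened, about 216 completers, 25% pooled loss (Sections 5 and 12.2). Mean change 4 mmHg, null change 2 mmHg, SD 10 mmHg, 5% significance, 90% power (synopsis and 12.2).

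**Reproducing the plan's figures.** The detectable difference is 4 − 2 = 2 mmHg. For a one-sided 5% test, the normal formula gives n = [10 × (1.645 + 1.282) / 2]² ≈ 214.1, so 215. The noncentral t calculation gives 216, with power 90.1%. The stated 216 is therefore reproduced on a one-sided basis. A two-sided test needs 265 and has 83.3% power at 216. For screening, 216 / 0.75 = 288 and 290 × 0.75 = 217.5, both consistent with 290.

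**The cap against the target.**
- Maximum entrants: 2 × 110 = 220.
- Losses allowed after Visit 2: 220 − 216 = 4, and 4 / 220 = 1.8%.
- Loss used in reaching the cap: 290 − 220 = 70, and 70 / 290 = 24.1%.
- Total loss from 290 to 216: 74, or 25.5%. The split is therefore 70 before Visit 2 and 4 after.
- If 216 means entrants, all 74 losses fall before Visit 2 and none is allowed afterwards.

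**If the cap fills.** Analysable patients = 220 × (1 − loss). Entrants needed for 216 = 216 / (1 − loss), rounded up. The loss rates are assumptions and mean no usable DBP data for the primary analysis.

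| Assumed loss after Visit 2 | Analysable of 220 | Power, one-sided, 2 mmHg null | Power, two-sided, 2 mmHg null | Entrants needed for 216 (per drug) |
|---|---|---|---|---|
| 2% | 215 | 89.9% | 83.1% | 221 (111) |
| 5% | 209 | 89.2% | 82.1% | 228 (114) |
| 10% | 198 | 87.7% | 80.0% | 240 (120) |
| 15% | 187 | 86.0% | 77.7% | 255 (128) |

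With independent losses, the chance of at least 216 analysable patients out of 220 is about 55% at 2% loss and 1.3% at 5%.

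**Against the test actually planned.** Protocol 12.5.2 and SAP 16.1.3 test for no change, the SAP code sets the null at zero, and SAP 6.5 makes tests two-sided by default. With a true change of 4 mmHg and SD 10, power exceeds 99.9% at 216, 209, 198 and 187.

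**The case against.** **The target is approximate.** The documents say approximately 216, so 213 or 209 is not clearly a breach. The 1.3% figure treats 216 as a hard threshold. This stands: the matching drop in power at 5% loss is about 1 percentage point (90.1% to 89.2%).

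**Discontinuing treatment is not the same as being lost to analysis.** Section 10 asks patients who leave early to complete the Visit 4 assessments, and Section 5.1 allows BP measurement at home. Some of these patients may still count in mITT. This stands in part. The limit of 4 applies to patients without usable DBP data, not to everyone who stops treatment. In the other direction, the Week 4 requirement in SAP 16.1.3 means that a missed Visit 3 also costs a patient.

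**The cap may never bind.** It closes entry only if more than 220 of 290 (75.9%) qualify at Visit 2, and the documents do not show that they will. This is true, but it does not rescue the target: with fewer than 220 entrants, even fewer losses can be absorbed. It does mean that raising the cap helps only if enough patients qualify.

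**Stronger readings.** A reader might infer that the cap makes the planned power unattainable and leaves the trial underpowered. The documents do not support this: the loss is modest on the basis used to size the trial and negligible for the planned test of no change. The mismatch between the sizing null of 2 mmHg and the tested null of zero is a separate matter. A reader might also infer that uncontrolled patients finishing the run-in will be turned away at a closed cap. No section provides for them, but this happens only if the cap fills while they are still in run-in, which is not shown.

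**Conclusion.** The inconsistency is real and the arithmetic is firm. A cap of 220 entrants and a target of about 216 completers agree only if about 1.8% or fewer of the entrants lack usable data, and the plan offers no basis for so low a rate. Section 12.2 adds to the problem by using 216 for entrants as well.

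The consequence is modest. If the cap fills, 5% to 15% loss gives about 209 to 187 analysable patients and 89% to 86% power on the plan's own sizing basis. These figures assume the loss rates shown and the plan's 4 mmHg change and 10 mmHg SD. The finding is that the stated number analysed and its power are unlikely to be delivered as written, not that the primary comparison is at risk. Severity: should-fix.

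**What to change.** In Section 12.2, Section 5, the synopsis and SAP 3.1:

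1. State whether 216 is the number entering the assessment period or the number with usable primary data at Visit 4, and use it the same way throughout.
2. Split the 25% into expected loss before Visit 2 and expected loss after it.
3. Then either keep 110 per drug and restate the expected analysable number and power (for example, about 198 and 88% at an assumed 10% loss, on the one-sided 2 mmHg basis), or set the Visit 2 entry cap to match the assumed loss within the 290 planned (for example, 114 per drug at 5% or 120 at 10%).

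The cap should not be defined on Visit 4 completers. Completion is known only 8 weeks after entry, so such a rule cannot tell sites when to stop, and it abandons the stated aim of balance at entry.

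Keeping the cap costs only wording, with slightly less favourable stated completers and power. Raising it costs more: 240 entrants at 10% loss is 82.8% of 290, and 255 at 15% is 87.9%, which leaves about 17% or 12% for all screening and run-in losses. The sponsor would need to show that this is realistic.

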### 5.1 **Procedures and Study Visits**

Patients will attend a total of 4 visits during the study. However, due to social restriction measures, the patients may not be able to visit the study site. In such cases, the Screening visit is a mandatory in-clinic visit and therefore must be performed at the study site. The Principal Investigator (PI) remains responsible for reviewing all study-related assessments.

The patients may not be able to visit the site to perform BP measurement for primary and secondary analysis, clinical laboratory tests, vital sign and physical examination, ECG, or other assessments required by the study flow chart. In such cases, these assessments will be performed by the health care professionals (study staff or qualified designee) at patient's home, if allowed by the country regulations.

The description of the activities, procedures, and tests to be performed at each visit is detailed below:

### 1. Screening and Start of Run-in Period (Visit 1, Week -4):

The following procedures/assessments must be completed during the screening on the same day prior to the run-in period (Visit 1):

- Obtaining informed consent.
- Checking inclusion and exclusion criteria.

MENARINI	Corporate Medical Department Protocol Template		ent
Identification Number	Version Number	State	Effective date
FORM-000050125	2.0, CURRENT	Effective	08 Jan, 2021

*Study Code:* MEIN/21/AmNe-Hyp/001

- Recording of medical history.
- Recording of prior and concomitant medications.
- Collection of demographic data.
- Recording concurrent diseases and medical conditions.
- Dispensing of antihypertensive treatment with NEB 5 mg or AML 5 mg monotherapy and dispensing of tablets for 4 weeks (run-in period) to eligible patients.
- Dispensing of written instruction for self BP measurement and patient diary.
- Dispensing of BP device.
- Physical examination and vital signs.
- BP measurement.
- ECG.
- Laboratory tests (see Section 8.2.3) (a follow-up phone call will be made within 24 hours in case of any abnormality and clinically relevant results from the laboratory tests according to the Investigator).
- Urine pregnancy test (UPT) (only for female patients).
- AEs and SAEs assessment.
- The patients meeting all inclusion criteria and none of the exclusion criteria will enter into the run-in period on the same day and will receive monotherapy of NEB 5 mg or AML 5 mg:
  - Patients who are already on therapy with NEB 5 mg or AML 5 mg will be provided with the same medication ie, NEB 5 mg or AML 5 mg, respectively.
  - Patients taking any other BBs or CCBse will be provided with NEB 5 mg or AML 5 mg.

### 2. Start of the Assessment Period (Visit 2, Week 0):

At the end of the run-in period (treatment with monotherapies for 4 weeks  $\pm 2$  days), only the patients with uncontrolled BP (SBP/DBP >130/80 mmHg), who tolerated the treatment and whose adherence to the therapy ranges from 80% to 120%, will enter the 8-week assessment period.

The starting of extemporaneous combination NEB 5 mg/AML 5 mg dosing is noted as Week 0.

The following procedures/assessments must be completed:

MENARINI	Corp	porate Medical Departm	ent
	Protocol Template		
Identification Number	Version Number	State	Effective date
FORM-000050125	2.0, CURRENT	Effective	08 Jan, 2021

*Study Code:* MEIN/21/AmNe-Hyp/001

- Recording of concurrent diseases and medical conditions.
- BP measurement.
- Compliance assessment by return of NEB and AML tablets (also empty blisters) and accountability.
- Study treatment dispensing (patients will be provided with the extemporaneous combination NEB 5 mg/AML 5 mg).
- Recording of concomitant medications.
- Physical examination and vital signs.
- UPT (only for female patients).
- AEs and SAEs assessment.
- Dispensing of written instruction for self BP measurement and patient diary.
- Return of written instruction for self BP measurement and patient diary dispensed at Visit 1 to site.

### 3. Assessment Period (Visit 3, Week 4):

During the assessment period, patients with controlled BP at Visit 3 (Week 4) will continue to receive NEB/AML 5/5 mg while patients with uncontrolled BP (SBP/DBP >130/80 mmHg) will receive the extemporaneous combination NEB 5 mg/AML 10 mg dosing.

The following procedures/assessments must be completed:

- Recording of concurrent diseases and medical conditions.
- BP measurement.
- Compliance assessment by return of NEB and AML 5 mg tablets (also empty blisters) and accountability.
- Study treatment dispensing (patients will be provided with the extemporaneous combination NEB 5 mg/AML 5 mg [in patients with controlled BP] or NEB 5 mg/AML 10 mg [in patients with uncontrolled BP]).
- Recording of concomitant medications.
- Physical examination and vital signs.
- UPT (only for female patients).
- AEs and SAEs assessment.
- Dispensing of written instruction for self BP measurement and patient diary.
- Return of written instruction for self BP measurement and patient diary dispensed at Visit 2 to site.

MENARINI	Corp	orporate Medical Department	ent
	Protocol Template		
Identification Number	Version Number	State	Effective date
FORM-000050125	2.0, CURRENT	Effective	08 Jan, 2021

*Study Code:* MEIN/21/AmNe-Hyp/001

### 4. End of the Assessment Period (Visit 4, Week 8):

The end of assessment period will be considered as end of 8 week  $\pm$ 4 days treatment with the extemporaneous combination NEB 5 mg/AML 5 mg and NEB 5 mg/AML 10 mg.

The following procedures/assessments must be completed:

- Recording of concurrent diseases and medical conditions.
- Recording of concomitant medications.
- Physical examination and vital signs.
- BP measurement.
- ECG.
- Laboratory tests (a follow-up phone call will be performed within 24 hours in case of any abnormality and clinically relevant results from the laboratory tests according to the Investigator).
- UPT (only for female patients).
- Compliance assessment by study treatment (extemporaneous combination of NEB 5 mg/AML 5 mg and NEB 5 mg/AML 10 mg) return (also empty blisters) and accountability.
- AE and SAE assessment. In case of any patients having an ongoing AE or SAE at the end of the treatment, there will be a follow-up telephone call after 2 weeks to ensure patient safety.
- Return of written instruction for self BP measurement and patient diary dispensed at Visit 3 to the site.
- Return of BP device (dispensed at Visit 1) to the site.

### **6** SELECTION OF PATIENTS

### 6.1 Informed Consent Process

The patient's written informed consent to participate in the trial must be obtained before any trial-related activities are carried out. Adequate information must therefore be given to the patient by the Investigator before informed consent is obtained (a person designated by the Investigator may give the information, if permitted by local regulations) The patient's written, dated and signed informed consent shall be obtained to the confidential disclosure, processing and transferring necessary documentation of the patient's health and personal data to the

MENARINI	Corpo	orate Medical Departn	nent
	Protocol Template		
Identification Number	Version Number	State	Effective date
FORM-000050125	2.0, CURRENT	Effective	08 Jan, 2021

*Study Code:* MEIN/21/AmNe-Hyp/001

Clinical Research Organization (CRO), Sponsor and its Affiliates, the competent Health Authorities (HA) and any other institutions, as legally required and in accordance with the local applicable privacy laws (for the Privacy information to be reported on the informed consent form [ICF] refer to Section 17).

The institution and the Investigator have the responsibility to duly inform patients about personal data processing and the relevant applicable privacy rights before their participation into the study.

After being duly informed and interviewed by the Investigator, the patient freely has to date and sign the ICF before being enrolled into the study and before undergoing any study procedure. The Investigator must store the original of the signed ICF in the Investigator's File, and the patient will be provided with a copy of it. If a protocol amendment would affect the terms of the ICF, it will be revised to reflect the protocol change and submitted to HA and Ethics Committee (EC) for approval. The Investigator will ensure that this new consent form is signed by all patients subsequently entered in the study and those currently in the study, if affected by the amendment.

Initial informed consent signature must be provided at site. Should the patient need to reconsent if permitted by investigative site procedures and local regulations, in case of social restrictions (Coronavirus Disease-2019 [COVID-19] pandemic), the ICF can be mailed to the patient. The patient can sign the consent form at home and mail it to the study site. Alternatively, the PI or designee can visit the patient at home to present the changes to the study and obtain their signature on the ICF at the patient's home. If the patient has any questions about the changes to the study prior to providing their signature, they will be provided with an opportunity to discuss these questions with the PI or designee. After having obtained the consent, a copy of the signed consent must be shared with the patient.

